#### Positivity rates (ELISPOT)

Positivity rates will be presented by treatment group for each visit along with the Clopper-Pearson 95% CIs.

#### Response rates

Response rates for RSV-specific ELISA and PRNT titers will be presented by treatment group for each post baseline visit along with the Clopper-Pearson 95% CIs. Response status is only applicable for subjects with a V1 (baseline) titer available.

The same type of analysis of response rates will be conducted for the ELISPOT results and for IFN- $\gamma$  and IL-4 results.

#### Responder rates (ELISPOT)

The responder rates (based on the total number of subjects with responder status available) will also be presented by group with exact Clopper-Pearson 95% CI.

### **3.5.8 Adverse Events**

A summary table by vaccination period and Overall will be presented as an overview of local and general solicited AEs and unsolicited AEs. This summary table will present the number and percentage of subjects who had at least one event in each period as well as the corresponding total number of events for:

- At least one AE documented
- Any TEAE
- Non-serious TEAEs
- SAEs
- Related TEAEs
- TEAEs Graded  $\geq 2$
- TEAEs Graded  $\geq 3$
- Related TEAEs Graded  $\geq 3$

- Related SAEs
- AEs leading to withdrawal from the trial
- AEs leading to withdrawal from second vaccination
- Deaths

The Overall summary is the sum of Period 1 and Period 2 counts.

A similar per subject table will be presented where each subject is counted once per their entire study participation.

For the ATP and FU Phase, all AEs will be listed by subject, including SOC and PT for the FAS. Any AE with onset later than 28 days since the previous vaccination will not be included in summary tables but will be included in the listing and will be flagged accordingly as non-treatment-emergent.

According to the clinical trial protocol no new AEs should be reported during the FU Phase, except SAEs and AEs related to respiratory tract infections, but if any are reported then they will be listed but considered non-treatment-emergent and no statistical testing or summaries will be presented for them.

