### **Treatment-Emergent Adverse Events (TEAE)**

An Adverse Event (AE) with onset either on the day of a vaccination, but after the vaccination or within the 28 days following a vaccination. Note that serious AEs are also considered treatment-emergent after 28 days (see below).

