### **Serious Adverse Events**

All Serious Adverse Events (SAEs) from first vaccination to last follow-up visit are considered as treatment-emergent regardless of the day of onset.

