### **AEs related to respiratory tract infections**

New AEs related to respiratory tract infections will be assessed and documented at all trial visits, including the FU Visits and are considered as treatment-emergent regardless of the day of onset.

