### **Serious Adverse Events**

All SAEs (solicited and unsolicited) with onset from first vaccination up to and including EAP will be summarized by SOC and PT by vaccination period. Related SAEs will be presented in similar fashion. SAEs which occurred during the FU Phase will be listed.

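### Main SAP 3.5.8 applies the 28-day cut-off to every adverse event, contradicting its own rules for serious and respiratory-infection events; vaccination period 2 has two end points

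*SAP*

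**What the plan says.** All references are to the main-study SAP unless stated.

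- **General Definitions.** A treatment-emergent event starts after a vaccination and within 28 days of it. Two event types are exempt from the limit. For SAEs: "All Serious Adverse Events (SAEs) from first vaccination to last follow-up visit are considered as treatment-emergent regardless of the day of onset". New respiratory-tract-infection events are documented at all visits, "including the FU Visits and are considered as treatment-emergent regardless of the day of onset".
- **Section 3.5.8, general text.** "Any AE with onset later than 28 days since the previous vaccination will not be included in summary tables". The same sentence goes on to say what happens to these late events instead: they are left out, "but will be included in the listing and will be flagged accordingly as non-treatment-emergent". The sentence names no exception. The following paragraph notes that "no new AEs should be reported during the FU Phase, except SAEs and AEs related to respiratory tract infections".
- **Section 3.5.8, Serious Adverse Events.** SAEs "with onset from first vaccination up to and including EAP will be summarized by SOC and PT by vaccination period". SAEs in the follow-up phase are listed.
- **Section 3.5.8, Unsolicited AEs.** Treatment-emergent events in the active phase are tabulated; non-treatment-emergent events appear in the listing only.
- **Section 3.5.8, per-subject overview.** "A similar per subject table will be presented where each subject is counted once per their entire study participation".
- **End of vaccination period 2.** The Vaccination Period definition gives 28 days after the second vaccination, or discontinuation if earlier. Section 3.3.3 assigns events up to and including EAP to period 2. The Active Trial Phase definition puts EAP at V3 + 28 to 35 days.

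**The concern.** Treatment-emergent status decides which table an event enters, so it needs one rule. Here the analysis section takes back what the definitions grant, and nothing says which prevails. The SAP also says that its analyses will be followed completely.

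Two programmers could each defend a different status for a late SAE or respiratory event. For onsets on days 29 to 35 after a dose they could also produce different SAE tables (14.3.2.1 to 14.3.2.4), unsolicited treatment-emergent tables and overview rows. SAE occurrence is the first-listed secondary safety endpoint (section 1.4.2). If SAEs are few, moving one between table and listing is visible.

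**Working it through.** No sample size or error rate is involved. The check sets the rules side by side and counts days from the visit windows.

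**Four example events under each rule**

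| Event | General Definitions | 3.5.8 general sentence | Specific 3.5.8 subsection |
|---|---|---|---|
| SAE, day 30 after a dose, before V3 or EAP | Treatment-emergent | Out of tables, flagged not emergent | In SAE tables |
| Non-serious respiratory-infection event, same timing | Treatment-emergent | Out of tables, flagged not emergent | In unsolicited tables, because emergent and in active phase |
| Any other non-serious event, same timing | Not emergent | Out of tables, flagged not emergent | Listing only |
| SAE in follow-up | Treatment-emergent | Out of tables, flagged not emergent | Listed only |

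Rows 1 and 2 conflict on both flag and table. Row 3 is consistent throughout. In row 4 the two parts of 3.5.8 agree that the event stays out of the SAE tables by system organ class; what conflicts is the flag, and whether the event counts in the per-subject overview, which covers the whole of participation and has rows for treatment-emergent events, SAEs and deaths.

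**Period assignment.** After dose 1, the Vaccination Period definition and 3.3.3 agree that period 1 runs to the second vaccination when one is given. After dose 2 they differ. Take an SAE on day 30 with EAP on day 35: 3.3.3 places it in period 2; under the definition period 2 closed on day 28, so the event has no period, although the SAE subsection tabulates it by period. Because 3.5.8 forms the overview's overall count by adding periods 1 and 2, an event without a period would drop from that count as well.

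**Length of the conflict.** Windows from the trial schedule (main SAP section 2; protocol 1.6): V3 = V1 + 28 to 35 days; EAP = V3 + 28 to 35; FU2 = V3 + 182 to 210.

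- Table conflict after dose 1 = (V1 to V3) − 28: from 28 − 28 = 0 to 35 − 28 = 7 days.
- Table conflict after dose 2 = (V3 to EAP) − 28: 0 to 7 days in the same way.
- At the target visits (weeks 4 and 8) both are 0.
- Flag conflict after dose 2 = (V3 to FU2) − 28: from 182 − 28 = 154 to 210 − 28 = 182 days. Most of this is follow-up, where the SAE-table rules agree.

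**Sponsor's later wording.** Booster SAP 4.5.8 carries the same sentence restricted to non-serious events, so the SAE exception is stated there.

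**The case against.** The best defence is that the SAP can be read coherently. Treatment-emergent is a defined term; the SAE and respiratory definitions disregard onset day in terms; the Unsolicited AEs subsection excludes by status rather than by day; and the SAE subsection is a specific rule that should prevail over a general sentence. The paragraph on follow-up reporting sets the same two event types apart. This stands as evidence of intent. It does not remove the contradiction: that paragraph concerns what should be newly reported in follow-up, does not amend the sentence before it, and does not reach days 29 to EAP, where the tables conflict.

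A second defence is that the consequences are small, and this largely stands. The endpoint for unsolicited non-serious events is itself limited to four weeks after each vaccination (section 1.4.2), so for non-serious respiratory events the cut-off matches the endpoint and only the treatment-emergent tables are inconsistent. The Phase I trial summarised in protocol 2.6 had no SAEs in 63 subjects.

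A reader might also infer more than the documents support:

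- *That SAEs go unreported.* The general sentence itself sends late events to the listing, and listings 16.2.7.2.1 and 16.2.7.2.2 cover SAEs.
- *That listing follow-up SAEs without tabulating them is an error.* Both parts of 3.5.8 agree on it.
- *That all events of days 29 to 35 are misclassified.* Other non-serious events are not treatment-emergent under any rule. Lying inside period 1 does not make an event treatment-emergent, because period and status are separate attributes.
- *That up to a fifth of the active phase is affected.* The maximum, 7 + 7 = 14 of 35 + 35 = 70 days, is calendar time with both visits on the last permitted day. It is not a share of events, and the documents give no event rate.

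**Conclusion.** The contradiction is real and minor. As written, the general sentence in 3.5.8 would keep a day 29 to 35 SAE out of tables that the SAE subsection requires, and would mis-flag late SAEs and respiratory-infection events. Its reach in the tables is those two event types over 0 to 7 days after each dose; in follow-up it is the flag and the per-subject overview. The two end points for period 2 are a separate inconsistency of 0 to 7 days; for the treatment-emergent and SAE tables it matters only for the same two event types.

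The day counts assume that visits fall inside their windows. The conclusion also rests on the main SAP as supplied: the booster SAP's introduction cites an Addendum to it dated October 11, 2017, which was not available and may already settle the matter.

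**What to change.** First check the Addendum of October 11, 2017. If it does not resolve the point:

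1. In 3.5.8, limit the sentence to *any non-serious AE not related to a respiratory tract infection*. This matches the General Definitions, and for SAEs the booster SAP.
2. In the Vaccination Period definition, end period 2 at EAP for AE and SAE tabulation, to match 3.3.3 and the SAE subsection. Leave the 28-day treatment-emergent window for all other events unchanged.

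The per-subject overview needs no further wording, since 3.5.8 already says that it covers all of participation. If outputs are final, state in the clinical study report which rule was programmed. The cost is two wording corrections, or one statement in the report, with no new data and no new tables.

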### **Serious Adverse Events**

All SAEs (solicited and unsolicited) with onset from first vaccination up to and including EAP will be summarized by SOC and PT by vaccination period. Related SAEs will be presented in similar fashion. SAEs which occurred during the FU Phase will be listed.

### **Related Grade 3 Adverse Events**

All Grade 3 or higher related AEs will be summarized by vaccination period by PT for solicited AEs, and by SOC and PT for unsolicited AEs. Individual subject listings for Grade 3 or higher AEs will be presented.

### **Solicited Local Adverse Events**

Solicited local AEs will be summarized by PT after each vaccination, and broken down by maximum intensity. The incidence (i.e., the number of subjects developing a specified solicited local AE on the day of vaccination or over the seven days after each vaccination divided by the number of subjects per respective vaccination period) will be calculated. The incidence will also be calculated for any solicited local AE for each vaccination period, the overall vaccination period, by treatment and by age group. The incidence of Grade 2 or higher AEs will also be calculated as well as the incidence of Grade 3 or higher AEs.

The duration (in days) of the solicited local AEs will be summarized and presented in a listing. A similar table and listing will be presented for relative day of onset for solicited local AEs.

Study specific version: 1.0  
Study specific version Date: 31-May-17

All tables created for solicited local adverse events per vaccination period will be repeated but on a per subject basis, where subjects are counted once per each adverse event experienced.

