### **8.1.2.2 Solicited AEs**

In this clinical trial protocol solicited AEs are defined as all symptoms specifically listed in the memory aid provided to the subjects following each vaccination. After vaccination the subjects are requested to monitor and record local symptoms (i.e. erythema, swelling, induration, pruritus and pain at the injection site) as well as general symptoms (i.e. body temperature, headache, chills, myalgia, nausea and fatigue) in the memory aid daily for the day of vaccination and the following 7 days (Days 0-7, 8 day period).

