### **Vaccination Period**

A vaccination period is defined as the period starting at a given vaccination and ending 28 days after this vaccination or until the subject receives another vaccination or discontinues the trial with the following hierarchy:

- If subject receives both vaccinations, the second vaccination represents the end of vaccination period 1.
- The end of vaccination period 2 is 28 days after receiving the second vaccination, unless subject discontinues earlier. In this case, the discontinuation date represents the end of vaccination period 2.
- If subject discontinues before second vaccination, the discontinuation date represents the end of vaccination period 1.

As the intention is that all subjects will receive two vaccinations, two vaccination periods will be recorded per subject. The overall vaccination period starts from the beginning of period 1 and ends at the end of period 2.

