#### **3.2. Analysis Populations**

##### **3.2.1 Full Analysis Set (FAS)**

This is the subset of subjects who will have received at least one vaccination and for whom any post-baseline data are available. The primary analysis of safety and efficacy will be performed on this analysis set.

In the case where a subject might receive the wrong randomized treatment, safety summaries for this subject will be based on actual treatment received. However, for a subject randomized to Group 2 or Group 4, and who received only one vaccination instead of two, safety summaries for this subject will be based on their randomized treatment group.

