## **3.3. Data Definitions, Data Conventions and Handling of Missing Data**

### **3.3.1 Missing Immunogenicity Data**

Analysis of immunogenicity variables will be done on a valid case basis, i.e. for missing observations no imputation technique such as “Last observation carried forward” will be applied, since this could introduce an optimistic bias into the analysis.

For assay results that are below the detection limit, refer to [Table 1](#): Detection Limits (DL) in the general definition section.

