### **3.5.6 Compliance**

Compliance will be summarized for the FAS population with respect to:

- Number of subjects who received at least one vaccination
- Number and percentage of subjects who received vaccination 1
- Number and percentage of subjects with memory aid returned at vaccination 1
- Number and percentage of subjects who received vaccination 2
- Number and percentage of subjects with memory aid returned at vaccination 2
- Number and percentage of subjects who received both vaccinations

Separate listings for vaccine administration and memory aid will also be presented.

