### **Solicited General Adverse Events**

Solicited general AEs will be summarized in the same manner as solicited local AEs. In addition, a summary table will be produced for general AEs by vaccination period with reasonable possibility of relationship to trial vaccine, where relationship is defined as either possible, probable, definite, or missing. Also, the number of general AE events by intensity and relationship to trial medication will be presented by vaccination period. Each by vaccination period table will be repeated but on a per subject basis where subjects are counted only once per adverse event experienced.

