### **Solicited Local Adverse Events**

Solicited local AEs will be summarized by PT after vaccination, and broken down by maximum intensity. The incidence (i.e., the number of subjects developing a specified solicited local AE on the day of vaccination or over the seven days after vaccination divided by the number of subjects with memory aid completed) will be calculated. The incidence will also be calculated for any solicited local AE by treatment group. The incidence of Grade 2 or higher AEs will also be calculated as well as the incidence of Grade 3 or higher AEs.

The duration (in days) of the solicited local AEs will be summarized and presented in a listing. A similar table and listing will be presented for relative day of onset for solicited local AEs.

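### The main-trial denominator for solicited AEs keeps subjects who have no memory aid, so a missing aid normally counts as no reaction; the booster SAP uses a different denominator

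*SAP*

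**What the plan says.** Main SAP 3.5.8, under Solicited Local Adverse Events, defines incidence as the number of subjects with the event in the eight days from vaccination, "divided by the number of subjects per respective vaccination period". The next subsection extends this: "Solicited general AEs will be summarized in the same manner as solicited local AEs".

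Membership of that denominator follows from two definitions. The General Definitions state: "A vaccination period is defined as the period starting at a given vaccination and ending 28 days after this vaccination". It can end earlier with the next vaccination or with discontinuation. SAP 3.2.1 admits to the FAS anyone with "at least one vaccination and for whom any post-baseline data are available". Neither mentions the memory aid.

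The events themselves are tied to the aid. Protocol 8.1.2.2 says "solicited AEs are defined as all symptoms specifically listed in the memory aid provided to the subjects following each vaccination", and SAP 3.4.2 describes both the local and the general solicited AEs as reported in it.

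The main SAP expects that some aids may not come back. Its compliance table (3.5.6) includes "Number and percentage of subjects with memory aid returned at vaccination 1", with a matching line for vaccination 2. These counts are not used as a denominator. The missing-data section has no rule for an absent aid: 3.3.1 covers immunogenicity ("Analysis of immunogenicity variables will be done on a valid case basis") and 3.3.2 covers incomplete dates.

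The booster SAP (4.5.8) has a different rule. Its incidence is "divided by the number of subjects with memory aid completed", and general AEs follow the same method. Its section on alterations from the protocol (4.6) does not mention the change from the main SAP.

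**The concern.** A subject who was vaccinated, attended later visits and never returned the aid is in the FAS and in the vaccination period. That subject stays in the denominator and normally has no way into the numerator. The effect is an implicit imputation of no reaction, the most favourable value for safety. Elsewhere the same SAP leans the other way for AEs: 3.3.3 applies a worst-case principle to partly missing start dates, and an AE with missing causality counts as related.

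Safety and reactogenicity is a secondary objective, and the occurrence of solicited AEs is a named endpoint. The rates are also to be shown by treatment and age group, so unequal return between groups would carry into those contrasts. The booster subjects come from main-trial Groups 1 and 3, so reactogenicity after primary and booster doses would be reported on two different bases.

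**Working it through.** The documents attach no power, rate or sample-size figure to this point, so there is no stated number to reproduce. The check is direct algebra on the two denominators.

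**Inputs**
- Reaction rate *p*: 61.1% as an illustration, from injection-site pain in the Phase I elderly group (11/18, Protocol Table 9). This is an overall per-subject figure over two vaccinations. The lower values 22.2% (erythema in the same group) and 5% (an assumption) show how the effect scales.
- Share of vaccinated subjects with no aid, *m*: not in the documents; assumed 0 to 20%.
- Group size: 80 planned per arm.

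**Formulas**, if non-return is unrelated to reactions and non-returners' reactions are not captured elsewhere:
- Main SAP rate = *p* × (1 − *m*)
- Booster SAP rate = *p*
- Understatement = *p* × *m*, that is, a relative loss of *m*

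| *m* | Main SAP rate at *p* = 61.1% | Points low | Points low at *p* = 22.2% | Points low at *p* = 5% |
|---|---|---|---|---|
| 0% | 61.1% | 0 | 0 | 0 |
| 2% | 59.9% | 1.2 | 0.4 | 0.1 |
| 5% | 58.0% | 3.1 | 1.1 | 0.25 |
| 10% | 55.0% | 6.1 | 2.2 | 0.5 |
| 20% | 48.9% | 12.2 | 4.4 | 1.0 |

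**In counts.** With 80 vaccinated, 72 aids returned and 44 subjects reporting pain, the main rule gives 44/80 = 55.0% and the booster rule gives 44/72 = 61.1%.

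**Unequal return.** If one arm had 2% non-return and another 10%, equal true rates of 61.1% would appear as 0.611 × 0.98 = 59.9% and 0.611 × 0.90 = 55.0%.

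**Partial capture by another route.** If half of the non-returners' reactions reached the tables anyway, then at *m* = 10% the rate would be 0.611 × (0.90 + 0.10 × 0.5) = 58.0%, a loss of 3.1 points instead of 6.1.

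**Non-return related to reactions.** Let non-returners react at rate *q*. The true rate is *p*(1 − *m*) + *qm*. The main rule is low by *qm*, and the rule based on returned aids is high by (*p* − *q*)*m* when *q* is below *p*. The second is the closer of the two whenever *q* exceeds *p*/2. If non-returners had no reactions at all (*q* = 0), the main rule would be exact.

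**The case against.** Several points on the other side have force.

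- **No return rate is given.** A reader might infer that the main-trial rates are in fact biased low, and more so in some arms. The documents support only the conditional statement. With full return there is no bias, and in a randomised, subject-blinded trial nothing in the plan suggests that return will differ by arm.
- **The memory aid may not be the only route.** Staff record immediate AEs after at least 30 minutes of observation, ask about AEs at visits, and examine the injection site at Visits 2 and 4. The plan does not say whether a listed symptom found this way enters the solicited tables. The injection-site examination has its own listing (16.2.7.1.18). Some leakage into the numerator is possible, hence *normally* rather than *always* reaction-free.
- **The anchor is generous.** The 61.1% comes from 18 subjects and covers two vaccinations. A per-vaccination rate cannot exceed the overall one, so per-vaccination losses may be smaller. In per-subject tables, a subject who lacks one aid but reports the event on the other still counts.
- **The booster contrast.** A reader might infer that booster reactions will look more frequent than primary ones in the same people. No listed table sets solicited rates side by side for the same subjects. Main-versus-booster comparisons are specified for immunogenicity only, and booster subjects are a consenting subset who completed all main-trial vaccinations.
- **Dose choice.** A reader might also infer that the denominator distorts the dose decision. The primary objective is framed on immunogenicity. Safety enters the selection of booster groups, but no threshold on solicited AEs is stated.
- **Visibility.** Return is tabulated and the aids are listed, so a large shortfall would be seen.

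These points limit the size and consequences. They do not remove the difference between the two denominators, nor the absence of any main-SAP rule for a missing aid.

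**Conclusion.** The point holds in conditional form. As written, main SAP 3.5.8 counts a vaccinated subject with no memory aid as reaction-free unless the event was captured by another route. The relative understatement of a per-vaccination rate equals the share of missing aids, provided that non-return is unrelated to reactions and nothing is captured elsewhere. It is negligible for rare reactions or near-complete return, and reaches several points for a common local reaction with 5–10% non-return. The booster rates rest on a different basis, which matters for informal side-by-side reading only.

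One uncertainty cannot be resolved here. The booster SAP says that main-study analyses are also governed by an SAP Addendum dated October 11, 2017. It is not among the documents reviewed and may already settle the denominator. This is a change that should be made because it is cheap and removes an unstated best-case assumption; it does not call the trial's primary conclusions into question.

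**What to change.** Unless the October 2017 Addendum already does this, change main SAP 3.5.8 as follows, for solicited local and general AEs alike:

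- **Per-vaccination tables:** divide by subjects with a returned memory aid holding at least one entry for that vaccination. The entry requirement stops a blank returned aid from counting as no reaction.
- **Overall and per-subject tables:** divide by subjects with at least one such aid.
- **Definitions:** the main SAP speaks of aids returned and the booster SAP of aids completed, and neither defines its term. Use one definition in both.
- **Reporting:** show return by treatment group and vaccination beside the rates, and keep the all-vaccinated rate as a sensitivity analysis. If non-returners react no more often than returners, the two rates bracket the true one.

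The cost is a short paragraph in the SAP and some reprogramming; the return counts are already planned for the compliance table, although the check for at least one entry is new. Reported rates will be slightly less favourable, and they may be overstated if non-returners reacted less. If the main-study tables are already final, add the revised rates flagged as additional analyses, which the SAP's introduction allows.
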